Official Title: Newer Direct-Acting Anti-Viral Agents as Sole Therapy of
Porphyria Cutanea Tarda in Subjects With Chronic Hepatitis C

NCT03118674

IRB-Approved Date: 5/5/2020

Rare Diseases Clinical Research Network

Porphyrias Consortium

Newer Direct-Acting Anti-Viral Agents as Sole Therapy of Porphyria Cutanea Tarda in Subjects with Chronic Hepatitis C

This protocol is for research purposes only, and should not be copied, redistributed or used for any other purpose. The procedures in this protocol are intended only for use by the Porphyrias Consortium investigators in carefully controlled settings. The Study Chair of this study should be consulted before using or attempting any procedure in this protocol.

Study Chair:

[name] MD

Professor of Medicine, Molecular Medicine & Translational Science
Wake Forest School of Medicine

[name]
[name]
[contact]
[contact]

Email: [contact]

Table of Contents

1. Protocol Synopsis	3
1.1 Overview	5
2. Specific Aims (Hypothesis and Objectives)	6
3. Background	6
4. Study Design and Methods	7
4.1 Inclusion Criteria	9
4.2 Exclusion Criteria	9
4.3 Recruitment of Participants	10
4.4 Retention Strategies	11
4.5 Data Elements	11
4.6 Study Procedures	12
4.7 Schedule of Events	15
4.8 Investigational Product	16
5.0 Data and Safety Monitoring Plan	16
5.1 Study Oversight	17
5.2 Definitions and Standards	17
5.3 Expected/Known Risks/Discomforts/Adverse Events Associated with Study Intervention and Procedures: Definition of Expected Adverse Events	17
5.4 Reporting Timeline	19
5.5 RDCRN DMCC Adverse Event Monitoring System	20
5.6 Study Discontinuation	20
5.7 Subject Discontinuation	21
5.8 Data Quality and Monitoring Measures	21
5.9 Quality Control: Study Related Procedures	21
6. Statistical Considerations	22
7. Data Management	24
7.1 Registration	24
7.2 Data Entry	25
8. Human Subjects	25
8.1 GCP Statement	25
8.2 Benefits	25
8.3 Risks	25
8.4 Written Informed Consent	26
8.5 Process of Consent	26
9. References	28
10. Appendices	29
I. Sample Processing Instructions	29

1. Protocol Synopsis

Interventional Synopsis

Protocol Number:	7210
Protocol Title:	Newer Direct-Acting Anti-Viral Agents as Sole Therapy of Porphyria Cutanea Tarda in Subjects with Chronic Hepatitis C
Study Chair:	[name]
Statistician:	[name]; [name], MS
Consortium:	Porphyrias Consortium
Activation Date:	04AUG2017
Current Status:	Enrolling
Sample Size:	49
Target Enrollment Period:	3 years
Study Design:	Interventional, one arm, open label non-inferiority
Primary Study Objective:	To assess whether Harvoni alone is an effective therapy of active PCT (measured as resolution of active PCT by 7 months) in patients with Chronic Hepatitis C (CHC).
Secondary Study Objective(s):	To assess time to resolution of active PCT after initiation of treatment with Harvoni; To assess time course of normalization of urinary porphyrin profiles; To assess cure of chronic hepatitis c
Study Population and Main Eligibility/ Exclusion Criteria:	
Inclusion Criteria:
 
 1. Willing and able to give informed consent 2. ≥18 years of age 3. Symptoms and signs consistent with PCT and well documented biochemical diagnosis (urinary total porphyrin excretion > 500 mcg/g creatinine with HPLC pattern typical of PCT—predominance of 8- and 7-carboxyl porphyrins [>50% of total]) 4. Clinical diagnosis of PCT established by a study PI 5. Chronic hepatitis C: HCV RNA positive and quantifiable in serum detected within 90 days of enrollment, and documented HCV genotypes 1,4, 5, or 6 for which Harvoni is an approved therapy. 6. Women of child-bearing potential must be willing to avoid pregnancy and use an accepted and effective contraceptive method during treatment. 
Exclusion Criteria:
 
 1. Women who are pregnant or who are breast-feeding 2. Patients who have already started treatment of PCT with phlebotomy or low dose hydroxychloroquine or chloroquine, or who have been in such treatment in the past 30 days 3. Patients who have already started another treatment regimen for CHC, or who have taken such treatment in the past 30 days 4. HIV infection with CD4 counts at baseline less than 350/µL or with evidence of any active AIDS-defining illnesses 5. Ongoing active alcohol abuse, defined as a history of drinking more than 25 drinks of alcohol per week during most weeks in the prior 4 months (History of prior, but not current alcohol abuse will NOT be grounds for exclusion because we seek to treat subjects with PCT and CHC of the type typically seen in clinical practice)

	
 6. Any ongoing active IV drug use 7. Patients who are taking amiodarone or who have taken amiodarone within 60 days prior to enrollment 8. Patients who are taking, or within the prior 28 days have taken, rifampicin or St John's wort (Hypericum perforatum), both of which are P-gp inducers, which may significantly reduce the drug levels and therapeutic effects of Harvoni 9. Uncontrolled diabetes (Hgb A1c >9.5% within 60 days prior to enrollment) 10. Chronic hepatitis B 11. Autoimmune hepatic liver injury—autoimmune hepatitis, primary biliary cholangitis/sclerosing cholangitis or overlap syndrome 12. Alcoholic hepatitis 13. Other metabolic disorders of the liver, e.g. Alpha 1 antitrypsin deficiency with ZZ Pi type, Wilson's disease 14. Prior known or suspected drug-induced liver injury within 6 months of enrollment 15. Known or suspected hepatocellular carcinoma 16. On liver transplant list, or current MELD >12 17. History of liver transplant 18. Estimated GFR (creatinine clearance) <30 mL/min (per Sofosbuvir being cleared by the kidney) 19. Serum ALT or AST >10x upper limit of normal 20. Serum bilirubin >2 mg/dL (excluding patients with known or suspected Gilbert's syndrome) 21. Any other comorbid condition, which in the opinion of the investigator precludes participation 22. Incarcerated individuals
Treatment (if applicable)	
Agent-	Harvoni—ledipasvir, 90 mg + sofosbuvir, 400 mg
Dosage, schedule, route of administration-	1 tablet per day, oral, taken with or without food. 8 weeks for patients without cirrhosis, not previously treated with HCV GT1 and HCV RNA < 6 million IU/mL; 12 weeks for patients without cirrhosis; 24 weeks for patients with compensated cirrhosis.
Safety Issues-	The drug is well-tolerated and highly effective for cure of HCV
Primary Outcome Measures:	The primary endpoint will be resolution of active PCT, defined as normalization of plasma porphyrins (less than 0.9 mcg/dL) by 7 months after start of therapy.
Secondary Outcome Measures:	
Time to resolution of active PCT, defined as cessation of any new blisters or bullae and normalization of plasma porphyrins. Complete resolution of skin manifestations is expected to occur later than normalization of plasma porphyrins, because it takes time for healing of the skin fragility that predisposes of blister formation to occur.
 
Decrease of the sum of urinary uro- and hepta-carboxyl porphyrins to less than 100 mcg/g creatinine, and a normal urine porphyrin HPLC pattern.
 
Cure of CHC, defined as no detectable HCV RNA at end of treatment (EOT) and persisting for at least 12 weeks after EOT.

Statistical Considerations (sample size and analysis plan):	The primary study hypothesis is that the proportion of patients whose PCT resolves by 7 months will be non-inferior to the performance goal of 50%. The non-inferiority margin will be set to 10%; a difference from the performance goal judged to be both

	
clinically acceptable and well within the margin needed to assure that the performance of Harvoni is at established levels of benefit from conventional therapies. Thus, the null hypothesis tested by this study is $H_0: \pi \leq 0.40$, against the alternative hypothesis $H_1: \pi > 0.40$.
 
Sample size requirements are based on an exact test of a binomial proportion. Assuming that the study drug has a true success probability of 58%, 49 patients yield 80% power to reject the null hypothesis at a one-sided significance level of 0.05.

Sponsors (federal, state, foundation and industry support):	Gilead Sciences; National Institutes of Health (NIH)

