4.2 Exclusion Criteria

1. Women who are pregnant or who are breast-feeding
2. Patients who have already started treatment of PCT with phlebotomy or low dose hydroxychloroquine or chloroquine, or who have been in such treatment in the past 30 days
3. Patients who have already started another treatment regimen for CHC, or who have taken such treatment in the past 30 days
4. HIV infection with CD4 counts at baseline less than 350/ μ L or with evidence of any active AIDS-defining illnesses
5. Ongoing active alcohol abuse, defined as a history of drinking more than 25 drinks of alcohol per week during most weeks in the prior 4 months (History of prior, but not current alcohol abuse will NOT be grounds for exclusion because we seek to treat subjects with PCT and CHC of the type typically seen in clinical practice)
6. Any ongoing active IV drug use
7. Patients who are taking Amiodarone or who have taken Amiodarone within 60 days prior to enrollment
8. Patients who are taking, or within the prior 28 days have taken, rifampicin or St John's wort (*Hypericum perforatum*), both of which are P-gp inducers, which may significantly reduce the drug levels and therapeutic effects of Harvoni
9. Uncontrolled diabetes (Hgb A1c $>9.5\%$ within 60 days prior to enrollment)
10. Chronic hepatitis B
11. Autoimmune hepatic liver injury—autoimmune hepatitis, primary biliary cholangitis/sclerosing cholangitis or overlap syndrome
12. Alcoholic hepatitis

13. Other metabolic disorders of the liver, e.g. Alpha 1 antitrypsin deficiency with ZZ Pi type, Wilson's disease
14. Prior known or suspected drug-induced liver injury within 6 months of enrollment
15. Known or suspected hepatocellular carcinoma
16. On liver transplant list, or current MELD >12
17. History of liver transplant
18. Estimated GFR (creatinine clearance) <30 mL/min (per Sofosbuvir being cleared by the kidney)
19. Serum ALT or AST >10x upper limit of normal
20. Serum bilirubin >2 mg/dL (excluding patients with known or suspected Gilbert's syndrome)
21. Any other comorbid condition, which in the opinion of the investigator precludes participation
22. Incarcerated individuals

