The therapy will be Harvoni at the usual dose (90 mg of ledipasvir and 400 mg of sofosbuvir) and duration for CHC therapy. One tablet taken daily for 8 weeks for patients without cirrhosis, not previously treated with HCV GT1 and HCV RNA < 6 million IU/mL; 12 or 24 weeks, duration to be determined based upon clinical features and prior treatment experience. 8 or 12 weeks for subjects with or without cirrhosis, not previously treated with anti-virals for CHC, and 24 weeks for subjects with cirrhosis who were previously treated with anti-virals for CHC without having achieved SVR. During the first year study visits will be monthly, and this includes the treatment period of either 12 or 24 weeks. To assess cure of HCV infection, repeated HCV RNA levels at 3, 6, and 12 months after end of Harvoni therapy will be done, as well as annually thereafter. Evaluation by a hepatologist at follow up visits will be as needed, determined by the screening lab test results and by clinical and lab findings at follow-up visits.

Lab measures to be checked monthly during therapy will include CBC, CMP, plasma total porphyrins, urinary total porphyrins (with HPLC), and levels of HCV RNA in serum by quantitative PCR (Section 4.7 Schedule of Events).

Porphyrin specific lab tests will be performed at the UTMB Porphyria Laboratory; all other labs will be performed at Covance Laboratories.

Subjects who have their treatment discontinued for any reason will continue to be followed until the end of the study, including longer-term follow up visits, unless they withdraw consent. If a subject becomes pregnant during the study Harvoni will be discontinued. The outcome of the pregnancy will not be followed as part of this study. Pregnancy during the study should be reported as an SAE.

Longer-Term Follow-up:

12 months after beginning treatment, subjects will be asked to return every four months for one year, with repeat of interval history and physical examination (especially to reassess the status of cutaneous lesions of PCT) and the above studies.

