4.7 Schedule of Events

	Screening (-30 to -1 Days)	Day 0	Day 30	Day 60	Day 90	Day 120	Day 150	Day 180	Day 210	Day 240	Day 270	Day 300	Day 330	Day 360	Day 480	Day 600	Day 720
			(Window +/- 7 days)														
			M1	M2	M3	M4	M5	M6	M7	M8	M9	M10	M11	M12	M16	M20	M24
Consent	X																
Complete Medical History	X																
Interval Medical History		X	X	X	X	X	X	X	X	X	X	X	X	X	X	X	X
Physical Examination	X	X			X			X			X			X	X	X	X
Skin Assessment (including pictures)	X	X	X	X	X	X	X	X	X	X	X	X	X	X	X	X	X
Alcohol & Tobacco use questionnaires	X																
Adverse Event/SAE Review														Each visit			
Urine Pregnancy	X																
Anti-HCV antibodies	X																
PTT	X																
Hepatitis B Surface Antigen	X																
HIV-1/HIV-2 Antibodies	X																
Serum Ferritin	X																
Serum iron and TIBC	X																
Complete Metabolic Panel\$	X	X	X	X	X	X	X	X	X	X	X	X	X	X	X	X	X
INR**	X																
HbA1c	X																
Erythrocyte UROD enzyme activity*	X																
UROD mutation analysis*	X																
HFE genetic testing*	X																
Hematology with Differential#	X	X	X	X	X	[X]*	[X]*	X	X	X	X	X	X	X	X	X	X
HCV RNA	X	X				[X]*	[X]*	[X]									
Plasma Total Porphyrins	X	X	X	X	X	X	X	X	X	X	X	X	X	X	X	X	X
Spot Urine ALA, PBG, Total Porphyrins	X	X	X	X	X	X	X	X	X	X	X	X	X	X	X	X	X
Fibroscan (if available at institution)	X														X		X
Dispense Study Drug [€]		X	X	X	X	X	X	X	X								

Hematology (complete blood count): white blood cell count (WBC), red blood cell count (RBC), hemoglobin, hematocrit, platelet count

\$Comprehensive metabolic panel: sodium, potassium, chloride, carbon dioxide, calcium, BUN, creatinine, glucose, and liver panel, including total protein, albumin, total bilirubin (TBR), alanine aminotransferase (ALT), aspartate aminotransferase (AST), alkaline phosphatase (AP)

*If not previously done

**INR (if not done within 4 months of screening)

[€]Drug is only to be dispensed at months 2-6 if additional therapy is warranted

[X]* Samples at these time points will be obtained only in subjects with cirrhosis who 24 weeks of Harvoni therapy is indicated; [X] Samples at these time points will be obtained 3, 6, and 12 months after the end of Harvoni treatment, and annually till end of study or EOT

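### For previously untreated patients with compensated cirrhosis, the synopsis assigns 24 weeks of study drug and the specific rule in Section 4.6 assigns 8 or 12 weeks; nothing says which governs.

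*Combined protocol and SAP*

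**What the plan says.** **Synopsis, dosage row.** Three courses are listed. The 8-week and 12-week courses are both limited to patients without cirrhosis. The third is "24 weeks for patients with compensated cirrhosis". Prior hepatitis C treatment plays no part in that third line.

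**Section 4.6, Treatment and Follow-up Visits.** The paragraph gives several statements in turn:

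- The therapy is Harvoni at the usual dose "and duration for CHC therapy".
- The shortest course is introduced as "One tablet taken daily for 8 weeks for patients without cirrhosis", with further conditions on genotype, treatment history and viral load.
- A general clause allows 12 or 24 weeks otherwise, "duration to be determined based upon clinical features and prior treatment experience".
- A specific rule then covers those who are new to hepatitis C therapy: "8 or 12 weeks for subjects with or without cirrhosis, not previously treated with anti-virals for CHC".
- The longest course is kept for a narrower group: "24 weeks for subjects with cirrhosis who were previously treated with anti-virals for CHC without having achieved SVR".

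**Section 4.8.** Treatment lasts 8, 12 or 24 weeks according to usual clinical criteria, and 12 weeks is expected for the majority. The section states 24 weeks for patients with cirrhosis whose earlier treatment failed or was followed by relapse. It gives no duration for untreated patients with cirrhosis.

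**Section 4.7, footnotes.** "Drug is only to be dispensed at months 2-6 if additional therapy is warranted". A second footnote restricts some sampling to subjects with cirrhosis for whom 24 weeks is indicated.

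**Eligibility.** The liver-severity limits in Section 4.2 include "On liver transplant list, or current MELD >12" and a bilirubin ceiling of 2 mg/dL. Compensated cirrhosis is not an exclusion. Section 4 allows prior hepatitis C treatment but does not require it.

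**The concern.** The synopsis decides on cirrhosis alone. Section 4.6 decides on cirrhosis together with treatment history. The two rules agree for patients with cirrhosis in whom earlier treatment failed, and part company for patients with compensated cirrhosis who have never been treated.

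A site working from the synopsis and a site working from Section 4.6 could therefore give the same kind of patient courses that differ by a factor of two. Duration is a core instruction for the only study drug, and the trial is multi-site and listed as enrolling. The stake is patient care under a contradictory dosing instruction. It is not the validity of the primary test.

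**Working it through.** **1. Can such a patient enrol?** Yes. Section 4.2 excludes transplant listing, MELD above 12 and bilirubin above 2 mg/dL, none of which amounts to excluding compensated cirrhosis. Section 4 sets out a two-stage definition of cirrhosis, so these patients are expected. Being untreated for hepatitis C is no bar to entry. Section 4.6 itself provides for untreated subjects with cirrhosis.

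**2. What does each text assign to an untreated patient with compensated cirrhosis?**

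| Place | Rule that applies | Duration |
|---|---|---|
| Synopsis | Compensated cirrhosis, any treatment history | 24 weeks |
| Section 4.6, specific rule | Untreated, with or without cirrhosis | 8 or 12 weeks |
| Section 4.6, general clause | Clinical features and prior treatment | 12 or 24 weeks, to be determined |
| Section 4.8 | 24 weeks stated only for previously treated cirrhosis | None stated |

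The first two rows cannot both be followed. Whether 8 weeks is really open to this patient is unclear, because Section 4.6 first limits the 8-week course to patients without cirrhosis. The secure conflict is 12 against 24 weeks.

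**3. Size, at one tablet a day and 28 tablets per supply (Section 4.8).**

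- 12 weeks: 12 × 7 = 84 tablets; 84 / 28 = 3 supplies.
- 24 weeks: 24 × 7 = 168 tablets; 168 / 28 = 6 supplies.
- Ratio 168 / 84 = 2.0; difference 168 − 84 = 84 tablets, or 3 supplies.

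**4. Where the readings diverge.** Assume one supply per monthly visit from Day 0, ignoring the recommended spare week. Supplies 1 to 3 (Days 0, 30, 60) are common to both readings. Supplies 4 to 6 (Days 90, 120, 150) are given under one reading only. They fall in the months 2-6 window of the Section 4.7 dispensing footnote, which leaves the matter to whether more therapy is warranted.

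**5. Effect on the timetable.**

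- End of treatment falls at Day 84 or Day 168.
- Time off drug before the Month 7 visit (Day 210) is 210 − 84 = 126 days or 210 − 168 = 42 days.
- The earliest date for confirming hepatitis C cure, 12 weeks after treatment ends, is 84 + 84 = Day 168 or 168 + 84 = Day 252.

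The primary endpoint is counted from the start of therapy, so its date does not move.

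**6. Effect on the sample size.** The plan's stated power is 80.2%. The exact binomial probability of 26 or more successes in 49 at a true rate of 0.58 is 0.8015, which reproduces it. Treatment duration does not enter that calculation.

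**The case against.** The strongest reply is that the synopsis line is a compressed summary and the body of the protocol leans the other way. Sections 4.6 and 4.8 both tie 24 weeks to cirrhosis with prior treatment. The sampling footnote in Section 4.7 speaks of subjects with cirrhosis for whom 24 weeks is indicated, which suggests it is not automatic for all of them. Section 4.6 also has a discretionary clause, so it is not purely a fixed rule. There are practical safeguards too: a hepatologist evaluates every subject at baseline, a site investigator must authorise dispensing, drug is requested through one central project manager, and duration is referred to usual clinical criteria.

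Much of this stands as mitigation. It makes the synopsis look like the outlier and makes mechanical use of a single line less likely. It does not remove the conflict. The discretionary clause is followed at once by the specific assignment that contradicts the synopsis. Section 4.8 is silent on untreated patients with cirrhosis. No text ranks the body above the synopsis.

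Two limits are also fair. The dispensing footnote does not isolate the disputed supplies, since its window also covers Day 60, on which both readings agree. And the documents do not show harm from either duration. Cure of hepatitis C is defined from the end of treatment and can be assessed under both.

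**Conclusion.** The contradiction is real and sits in current text. For untreated patients with compensated cirrhosis, the synopsis and the specific rule in Section 4.6 differ by at least 12 weeks of study drug: 84 against 168 tablets, two-fold.

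The comparison takes 12 weeks as the Section 4.6 course, because the status of 8 weeks is unclear there. The visit-by-visit supply dates rest on the assumption in step 4. The documents give no expected number of such patients, and it may be small.

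The point must be fixed because it is a contradictory dosing instruction, and on that ground alone. The timing of the primary endpoint, N = 49 and the 26-success rule do not change. Which duration is right is not judged here.

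**What to change.** Reconcile the dosage row of the synopsis with Sections 4.6 and 4.8 so that all three state the same assignment and cover untreated patients with compensated cirrhosis by name. If clinical discretion is meant to prevail over the listed durations, the text should say so in each place. Then check that both Section 4.7 footnotes, on dispensing and on sampling, agree with the reconciled wording. The sponsor decides which duration and which criteria apply; none is proposed here.

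The cost is a wording amendment in three places and one consistency check. It adds no visits, procedures, data fields or analyses.

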1.1 Overview

The purpose of this study is to learn whether Harvoni, a simple oral treatment for chronic hepatitis C infection, is effective for treatment of porphyria cutanea tarda (PCT).

PCT is the most common form of porphyria in the USA and most other countries and regions of the world. There are two major types of PCT: acquired (type 1, which accounts for about 80% of cases) and inherited (type 2). The major risk factors for type 1 PCT are heavy alcohol use, iron overload, hepatitis C (HCV) or human immunodeficiency virus (HIV) infection, and ingestions of estrogens. Most patients with PCT, either type 1 or type 2, have one or more of these risk factors. In type 2 PCT, subjects have a partial deficiency, usually ~ 50% of normal, activity of the enzyme uroporphyrinogen decarboxylase (UROD), whereas, in type 1 PCT, the deficiency in UROD activity is limited to the liver, and it appears usually to be acquired and due to excess iron, alcohol, HCV, HIV, etc.

The time-honored treatment of first choice for either form of PCT has been iron reduction, usually carried out most quickly and efficiently by therapeutic phlebotomy. However, (hydroxy) chloroquine in low doses also is effective. There have been anecdotal reports of treatment of HCV infection with interferon with or without ribavirin being effective treatment. To date, however, there have been no prospective case series of such treatments, nor have there been comparisons of results with anti-viral treatments, compared with iron reduction or (hydroxyl) chloroquine.

With the recent development of newer and highly active and effective therapies for HCV infection, with fewer side-effects than were heretofore possible, we have felt that it now is time for a careful and formal study to assess whether these agents are effective treatments for PCT.

This is an open-label study with a non-inferiority design, to assess whether Harvoni is an effective treatment of PCT.

2. Specific Aims (Hypothesis and Objectives)

Aim: To assess whether Harvoni alone is an effective and durable therapy of active PCT in patients with CHC due to any genotype for which Harvoni is approved for treatment, currently genotypes 1, 4, 5, or 6. Genotype 1 HCV accounts for ~ 75% of chronic hepatitis C infections in the USA. Genotype 4 is common in Egypt; rare in the USA, but it does occur. Our goal is to be as inclusive as possible and to test effects of Harvoni treatment in real-world situations. We will test whether Harvoni treatment is non-inferior to previously published remission times of other standard treatments of PCT (low dose hydroxychloroquine or phlebotomy therapy) (Singal et al, 2012).

Hypothesis: Treatment of PCT associated with CHC with Harvoni is as effective and as durable as published data on the current standard treatments of iron reduction by phlebotomies or low dose hydroxychloroquine.

3. Background:

CHC is a well-known risk factor for PCT. Other risk factors include hepatic iron overload, often related to mutations of *HFE* associated with hereditary hemochromatosis, excess alcohol use, estrogen therapy, and HIV infection ([name] et al, 1998, 2013; Egger et al, 2002; Besur et al, 2014).

The standard of care therapy for PCT has been iron reduction by therapeutic phlebotomy, which has been effective in nearly all subjects, regardless of underlying major risk factors (Besur et al, 2014; [name] et al, 1998, 2013). Based upon more recent results, low-dose therapy with 4-aminoquinolones, (chloroquine and/or hydroxychloroquine), also has become a standard therapy, as has a combination of iron reduction and one of these agents (Stölzel et al, 2009; Singal et al, 2012; [name], unpublished). However, it has been found that decreases in measures of iron status following chloroquine therapy did not occur in subjects with *HFE* mutations and that C282Y +/- subjects did not respond very well to chloroquine (Stölzel et al, 2003). In addition, the use of 4-aminoquinolones, as against phlebotomy therapy, may be associated with earlier recurrence of active PCT after a course of therapy than after a course of iron reduction and maintenance of an iron-reduced state (Stölzel et al, 2003, 2009; & [name], unpublished observations). This led to the recommendation that, for those with *HFE*-linked hemochromatosis, therapeutic phlebotomy should remain the treatment of first choice (Stölzel et al, 2003).

During the past 20 years or so, there have been anecdotal reports of PCT resolving with successful anti-viral therapy of CHC, although there also have been reports of such therapy precipitating or worsening PCT ([name] et al, 2013). Because active cutaneous lesions of PCT are generally more symptomatic than CHC, which usually occurs with few, if any, symptoms until late in the course of advanced liver disease, and because typically PCT is successfully treated within about 6 to 7 months, either with iron reduction or one of the 4-aminoquinolones (Singal et al, 2012), the usual recommendation has been first to treat active PCT and thereafter to treat CHC. Until

recently, therapy of CHC has been longer (usually at least 48 weeks), less often successful and fraught with adverse effects, especially related to the use of interferon alpha, which has been the cornerstone of treatment. However, during the past few years, newer and more effective oral therapies for CHC, with far fewer and less severe side-effects have been approved by the US FDA, the EMA, and other regulatory agencies. In particular, sofosbuvir (Sovaldi) with interferon and ribavirin or with simeprevir (Olysio), and more recently, the combination of ledipasvir + sofosbuvir (Harvoni) (Gilead Sciences) have proven highly effective and to produce far fewer severe adverse effects than the earlier therapeutic regimens based upon interferon (usually in combination with ribavirin) (Syllabus of Post-Graduate Course and presentations at annual meeting of AASLD, Nov 7-11, 2014, Boston, MA). Other combinations of all oral, direct-acting antivirals have recently been approved (e.g., Viekira Pak, Abbvie; Mavyret, Abbvie; Zepatier, Merck) and/or are in late-stage clinical trials.

Because treatment for CHC is now highly successful within as short a time as 8-12 weeks and with few adverse effects, it is reasonable to consider this treatment first in patients with both CHC and PCT. However, experience is needed with a reasonable number of patients in order to validate this approach, and in particular to demonstrate that time to remission is as rapid and that remission of PCT is as durable following therapy with Harvoni as with phlebotomy or (hydroxy) chloroquine. Also, PCT is a heterogeneous, multifactorial disease, and it is important to ascertain whether other co-existing susceptibility factors influence response to a new treatment approach and durability of remission.

The Office of Rare Diseases (ORD) of the National Institutes of Health (NIH) established a Rare Diseases Clinical Research Network (RDCRN) in collaboration with other NIH Institutes and has funded several rare diseases clinical research consortia and one Data Management and Coordinating Center (DMCC). The Porphyrias Consortium was created as part of the RDCRN, to study the human porphyrias.

4. Study Design and Methods

This will be a one arm, open-label non-inferiority study of Harvoni for treatment of PCT complicating chronic hepatitis C infection caused by HCV genotypes for which Harvoni is approved as therapy, compared to a performance goal of a 50% remission rate at 7 months. This performance goal is based on recently published results from our Consortium (Singal et al, 2012), in which the median time to remission for subjects treated either with phlebotomy or hydroxychloroquine was 7 months, and on expert consensus that if Harvoni demonstrates a median time to remission of 7 months, porphyrias experts would consider using Harvoni over phlebotomy or hydroxychloroquine as a first line of treatment for PCT patients with Hepatitis C. Our aim is to be as inclusive as possible, so that the results will be as generalizable as possible to regular clinical practice. Comparison of response rates, both for amelioration of PCT (the primary endpoint) and for cure of HCV infection (a secondary

endpoint) will be by comparison to recently published results from our Consortium (Singal et al, 2012) and elsewhere (results of recent trials of Harvoni for treatment of chronic hepatitis C).

Adult subjects, of either gender with well-established PCT, who also have CHC due to an HCV genotype 1, 4, 5, or 6, for which Harvoni is approved as therapy, will be invited to take part. PCT patients with CHC typically have additional susceptibility factors, such as alcohol use, estrogen exposure, smoking, *HFE* mutations, *UROD* mutations or HIV infection ([name] et al, 1998, 2013; Egger et al, 2002), and none of these will be reasons for exclusion. Subjects previously treated for PCT and/or HCV infection will be eligible, provided they meet the current criteria for inclusion and exclusion.

Assessment of Stage of Liver Disease:

Cirrhosis will be considered to be present according to the following two-tiered approach:

Stage 1—based upon historical data:

- a. Any prior liver biopsy that was interpreted by a pathologist as showing definite or probable cirrhosis (Ishak fibrosis score of 5 or 6; or Metavir fibrosis score of 4); and/or
- b. Hepatic elastography/Fibroscan value, performed within the prior three years, that showed liver stiffness > 12.5 kPa.

Stage 2—for subjects without historical data:

- a. A liver biopsy performed on the subject that shows definite or probable cirrhosis (Ishak fibrosis score of 5 or 6; or Metavir fibrosis score of 4); and/or
- b. Hepatic elastography/ Fibroscan, performed for screening purposes, that shows liver stiffness greater than 12.5 kPa; and/or
- c. Hepatic imaging study (ultrasound, CT or MRI), performed within three months of enrollment that showed findings typical of cirrhosis, such as irregular, lobulated or nodular appearance of the liver, enlargement of the spleen, gastro-esophageal varices, ascites, or other evidence of portal hypertension; and/or
- d. Physical examination that shows findings typical of cirrhosis, such as multiple spider angiomas, red palms, prominent venous pattern of the upper abdominal wall, palpable and firm or hard liver, often with increased prominence of the left lobe, when accompanied by a decreased platelet count (<140,000/ μ L) in peripheral blood.

As is standard practice, if subjects use alcohol, they will be strongly encouraged not to consume alcohol in any form, at least for the duration of the study and its follow-up. They also will be asked to stop any use of estrogens; and those that smoke cigarettes will be advised to stop smoking. Adherence to these recommendations will be tracked by patient interviews. Continuing use of estrogens and/or smoking will NOT be grounds

for removal of subjects from the study. Subjects may have HIV infection, as long as their CD4 counts at baseline are greater than or equal to 350/ μ L and they do not have evidence of any active AIDS-defining illnesses.

